12.4. Immediately Reportable Events

The following medical events must be immediately reported to the Sponsor:

- SAE
- Pregnancy

Emergency contact information can be found in Table 1.

12.4.1. Serious Adverse Event

If the Investigator or study center staff becomes aware of a SAE that occurs in a study subject after first administration of study drug through 30 days following the last dose of the study medication, this must be reported within 24 hours to PPD-PVG, the medical monitor, and Sunovion responsible physician whether considered related or unrelated to the study drug. SAEs must be recorded on the CRF and the data recorded should agree with that on the SAE form.

Following the end of subject participation in the study, the Investigator or an authorized delegate should report SAEs “spontaneously” to the PPD-PVG if considered at least possibly related to the study drug.

SAEs will be followed until resolution, loss to follow-up, stabilization of condition, or the event is otherwise explained.

In addition to the initial telephone notification, an initial SAE form as applicable must be completed and signed and sent via fax or email (see [Table 1](#)) to PPD-PVG within 1 business day of the Investigator or study center staff becoming aware of the event. The SAE form must be signed by the Investigator or appropriate designee. The Sponsor provides the SAE form used to report SAEs.

The Sponsor or designee will promptly notify all study centers and Investigators of a SAE that is determined to be expedited to the Regulatory Authorities in accordance with applicable law(s) and regulation(s). These SAEs must be promptly reported to the Institutional Review Board (IRB) by the Investigator or the appropriate person at the study center if required per IRB guidelines.

12.4.2. Pregnancy

Pregnancies that occur from the time that informed consent is signed through 30 days following the last dose of the study medication will be collected and reported on the Pregnancy Event Form.

If a subject becomes pregnant during the course of the study, she will be instructed to immediately stop taking the study medication. Further, the subject will be instructed to return promptly/within 48 hours of the first notification of pregnancy to the research site and undergo a serum pregnancy test, as confirmation of pregnancy. If positive, the subject will no longer receive any additional study medication. All pregnancies, whether or not the subject received any additional study medication, will be followed until resolution (ie, termination [voluntary or spontaneous] or birth).

If a pregnancy is reported for the study subject's partner, the study subject must agree to complete abstinence for the duration of the study or until resolution of the pregnancy, whichever comes first, or discontinue study drug and withdraw from the study. If the subject chooses to withdraw from the study, continued abstinence is recommended for 30 days after the last dose of study medication.

To report a pregnancy, the Pregnancy Event Form must be completed and sent via fax to PPD-PVG within 1 business day of the Investigator or study center staff becoming aware of the pregnancy. The Sponsor provides the Pregnancy Event Form.

If the subject received blinded study medication, unblinding of the study medication will be offered to the subject when knowledge of such treatment may have an impact on further treatment decisions. Otherwise, information regarding to what treatment the subject was assigned may be provided when the study has ended.

Pregnancy itself is not regarded as an AE unless there is a suspicion that the study drug may have interfered with the effectiveness of a contraceptive medication or other AEs were detected.

12.5. Data Monitoring Committee/Data and Safety Monitoring Board

The Data and Safety Monitoring Board (DSMB) will monitor safety throughout the study (and may review blinded, partially blinded, or unblinded data). The DSMB will be independent of the Sponsor, CRO, and the Investigators and will be empowered to recommend stopping the study due to safety concerns but not for efficacy or futility. The membership of the DSMB and its mandate will be described in a separate DSMB charter.

13. TERMINATION OF SUBJECT FROM STUDY/DISCONTINUATION OF STUDY DRUG

13.1. Criteria for Study Drug Discontinuation

Subjects may be discontinued from the study drug at any time during the treatment period. The possible reasons for discontinuation of study drug are as follows:

- Adverse event
- Lack of efficacy (specify)
- Lost to follow-up (specify)
- Non-compliance with study drug (specify)
- Protocol violation (specify)
- Pregnancy
- Withdrawal by subject (specify)
- Other (specify)

If, at any time during the course of the treatment period, in the opinion of the Investigator, the subject may no longer safely participate due to a change in medical status (eg, experiences an AE, becomes pregnant), the subject must be discontinued from the study drug.

The primary reason and information for study drug discontinuation will be recorded on the appropriate CRF. In case of death, the date of death should be captured on the CRF.

13.2. Criteria for Subject Termination from the Withdrawal Period

Subjects may terminate during the withdrawal period for any reason.

The possible reasons for termination during the withdrawal period are as follows:

- Adverse event
- Lost to follow-up (specify)
- Pregnancy
- Withdrawal by subject (specify)
- Protocol deviation (specify)
- Other (specify)

The reason for termination during the withdrawal period will be recorded on the appropriate CRF.

Subjects who prematurely terminate study participation will not be replaced.

13.3. Clinical Assessments After Study Drug Discontinuation

Subjects who discontinue study medication before completion will be asked to return to the site and complete the EOT visit assessments ([Section 11.8.9](#)), as soon as possible following discontinuation of study drug, and complete the study medication withdrawal assessments and visits ([Section 11.8.10](#)).

14. STUDY TERMINATION

The Sponsor reserves the right to discontinue the study at this study center or at multiple centers for safety or administrative reasons at any time while safeguarding that early termination does not compromise subjects' safety or well-being. In particular, a study center that does not recruit at an acceptable rate may be closed. Should the study be terminated and/or the study center closed for whatever reason, all documentation and study medications pertaining to the study must be returned to the Sponsor or its representative.

If, in the opinion of the Investigator, clinical observations suggest it may be unsafe to continue, the Investigator may terminate part or the entire study at his or her site after consultation with the Sponsor.

In the event of study or site termination, subjects will be asked to return to the site and complete the EOT visit assessments ([Section 11.8.9](#)) as soon as possible after discontinuation of study drug.

15. STATISTICS

The Statistical Analysis Plan (SAP) will provide details on the statistical methods planned for this study and will be finalized before data base lock.

15.1. Sample Size

The sample size for this study was estimated based on 2 hypotheses associated with the primary efficacy endpoint (change from baseline in number of binge days per week at Week 12). A fixed sequence closed testing procedure was used to adjust for 2 comparisons of dasotraline doses vs placebo (ie, with dasotraline 6 mg vs placebo tested first and dasotraline 4 mg vs placebo tested after if the previous one is significant at the 0.05 level) for the sample size justification. Based on the Study SEP360-221 results, assuming a common standard deviation (SD) of 1.75 and a mean improvement of 0.9 (effect size 0.517) and 0.8 (effect size 0.457) over placebo for change from baseline in number of binge days per week at Week 12 for dasotraline 6 mg/day and 4 mg/day doses, respectively, a sample size of 96 subjects per treatment group will provide at least 85% conjunctive power to reject both null hypotheses. An upward adjustment of approximately 40% is assumed to compensate for subjects who are randomized but discontinue from the study, thus, a total sample of 480 subjects (160 subjects per group) will be randomized with a ratio of 1:1:1 for placebo, and dasotraline 4 mg/day and 6 mg/day, respectively. The sample size calculation was based on Monte Carlo simulation from EAST 6.4.

15.2. Statistical Hypotheses

The hypotheses associated with the primary endpoint and key secondary endpoints will be tested using a testing procedure in [Section 15.4.1.4](#).

Primary Hypotheses

In adults with moderate to severe BED, after 12 weeks of treatment,

- Dasotraline 6 mg/day reduces change from baseline in the number of binge days per week relative to placebo
- Dasotraline 4 mg/day reduces change from baseline in the number of binge days per week relative to placebo

Key Secondary Hypotheses

In adults with moderate to severe BED, after 12 weeks of treatment, 6 mg/day dasotraline or both doses of dasotraline:

- Reduce change from baseline in BE-CGI-S score relative to placebo
- Provide a greater proportion of subjects with a 4-week cessation from binge eating at Week 12 relative to placebo
- Reduce change from baseline in Y-BOCS-BE total score relative to placebo

15.3. Analysis Populations

Intent-to-Treat (ITT) Population: All randomized subjects who receive at least one dose of study medication and have at least 1 post-baseline result in any efficacy evaluation. The ITT population is the primary population for efficacy analyses, ie, unless otherwise specified, all efficacy analyses will be based on ITT population.

Per-Protocol (PP) Population: All ITT subjects who have no major protocol violations that may affect the interpretation of the primary efficacy endpoint.

The PP population will be used to assess robustness of the primary efficacy analysis. Major protocol violations and the PP population will be determined through a blinded data review meeting and identified prior to the database lock.

Subjects in the ITT and PP populations will be analyzed based on the treatment to which they are randomized.

Double-blind (DB) Safety Population: All randomized subjects who receive at least one dose of study medication.

The DB Safety population mainly will be used for the data analyses of the safety data collected through Week 12 or during the treatment period. Subjects will be analyzed based on the predominant treatment received, in the event that a subject receives a treatment other than the one to which he or she is randomized. The predominant treatment is defined as the treatment (ie, placebo, dasotraline 4 mg/day, or dasotraline 6 mg/day) to which the subject is exposed for the greatest duration during the treatment period. The predominant treatment will generally be the same as the randomized treatment group, unless the subject takes incorrect study medication during the entire study.

Withdrawal Safety Population: The Withdrawal safety population includes all randomized subjects who receive at least one dose of study medication, and either discontinue the study drug during the treatment period before the Week 12 visit or complete the 12-week treatment period but do not enter the extension study (Study SEP360-322), and have at least one assessment after the last dose of study medication for any safety or efficacy evaluation. The Withdrawal safety population mainly will be used to summarize the assessments collected in the withdrawal period.

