Baseline Visit (Day -1): Subjects who meet eligibility criteria at Screening will return to the study site on Day -1 for confirmation of screening evaluations as well as completion of predose assessments and procedures including clinician review of the daily binge eating diary. Any lapse in diary completion during the 14 day period (eg, 1 or more days are skipped) will be discussed with the subject. If 1 or 2 days per week are incomplete or missing, the subject may complete the diary with the clinician. However, if the subject cannot recall enough information to complete the diary in full after clinician review, the subject will be ineligible. Subjects will also be ineligible for randomization if there are more than 2 missed diary days in 1 week. Eligible subjects (based on confirmation of study entry criteria) will be randomized and dispensed study drug at Day -1.

Treatment Period (Day 1 [Week 0] through Day 84 [Week 12]): Subjects will self-administer the study drug on an outpatient basis once a day with or without food beginning on Day 1, the day after the Baseline visit, and continue for 12 weeks. Subjects will be instructed to administer study drug at approximately the same time each morning including on days when clinic visits occur. During the treatment period subjects will continue to complete a daily binge eating diary, which will be reviewed at each visit. During the treatment period, subjects will have one clinic visit every week for the first month, then one clinic visit every 2 weeks thereafter. In order to facilitate scheduling of clinic visits, a window of ± 2 days will be allowed for each weekly clinic visit and a window of ± 3 days will be allowed for each biweekly clinic visit, and a window of ± 1 day for the end of treatment (EOT) visit and each clinic visit of the withdrawal period.

Subjects who complete the 12-week Treatment Period may be eligible for participation in the open label extension study (SEP360-322). For subjects enrolling in the open label extension study, Week 12 will be the last visit for this study.

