Study Medication Withdrawal Period (Day 85 through Day 105 [Week 15]): Subjects who do not enroll in the extension study for whatever reason, eg, less than 12 weeks treatment in this study, lack of interest in the extension study, or failure to meet all eligibility criteria for the extension study will return to the clinic at Weeks 13, 14, and 15, to assess safety and potential study medication withdrawal effects during the study medication withdrawal period. Subjects who discontinue from study drug before completion of the 12-week treatment period will be asked to return to the clinic and complete the End of Treatment visit as soon as possible following discontinuation of study drug and complete the 3 week withdrawal period. In addition, subjects will continue to complete the binge eating diary during this period.

Assessment of potential withdrawal effects will be conducted via administration of the CSSA, DESS, HAM-A, and MADRS at Week 12 (End of Treatment), then again at Weeks 13, 14, and 15 during the 3-week study medication withdrawal period.

The CSSA and DESS will also be completed during the 3-week study medication withdrawal period on non-clinic visit days. Clinical site staff will call the subject every other day during the study medication withdrawal period, beginning the second day after the last dose of study drug, unless a clinic visit is scheduled for that day (up to 3 times per day if the clinical site staff are unable to contact the subject on the first 2 attempts). Clinical site staff will record the responses in the subject's source information and in the CRF with the contact date and time.

A window of ± 1 day will be allowed for each weekly clinic visit and telephone call. If the subject cannot be contacted on a given day, during the next contact the study site staff will retrospectively collect the missed CSSA and DESS, in addition to the current day's CSSA and DESS.

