The Withdrawal Population: The withdrawal population includes all randomized subjects who receive at least one dose of study medication, and either discontinues the study drug during the treatment period before the Week 12 visit or completes the 12-week treatment period but do not enter the extension study (Study SEP360-322), and have at least 1 assessment after the last study drug for any safety or efficacy evaluation. The withdrawal population mainly is used to summarize the safety/efficacy assessments collected in the withdrawal period except of adverse event data.

The Modified Withdrawal Population: all subjects in the withdrawal population plus the subjects who do not enter the extension study and do not enter the withdrawal period, but the last study dose dates are at least 2 days earlier than the last study visit. The modified withdrawal population will be mainly used for adverse event that could be retrospectively collected.

Withdrawal analyses will be presented by planned treatment group for efficacy data and by actual treatment group for safety data.

Pharmacokinetics (PK) Population: The PK population is defined as all subjects who are randomized, receive at least 1 dose of study drug, and have any post-baseline plasma concentrations sample collection of dasotraline.

6.1.10 Stratification Factor ‘Baseline Number of Binge Days’ vs. Baseline Number of Binge Days Group

Group of Baseline number of binge days is defined as: Baseline number of binge days ≤ 4 , Baseline number of binge days >4 ; this group should be essentially equivalent to the stratification factor unless there is a subject stratified into the incorrect stratum. The stratification factor (ie, Baseline binge days category) will be consistently used in the statistical models, when applicable, for efficacy analysis as described in this document. Compared with the stratification factor, group of Baseline number of binge days will be used in the other scenarios, including the statistical models based analyses for safety variables.

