7.4.7.2 Withdrawal Period

The number and percentage of subjects with following categories will be summarized by treatment for any post-withdrawal baseline for withdrawal population.

- each type of suicidal ideation,
- any suicidal ideation,
- each type of suicidal behavior,
- any suicidal behavior,
- any having self-injurious behavior without suicidal intent,
- any suicidality

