7.4.8.3.2 Events Subject to Additional Monitoring (ESAMs)

In addition to monitoring for irregularities in medication handling, AEs that may be suggestive of a developing abuse potential, will receive special attention. The adverse experiences or related signs and symptoms that will require additional monitoring (ESAMs) are listed in [Attachment 9.6](#). AEs identified as ESAMs will be summarized by ESAM type and PT by treatment for safety population (treatment period) and withdrawal population (withdrawal period), respectively. ESAMs will also be listed for all randomized subjects.

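### The End of Treatment visit alone can meet the Withdrawal Population rule, so subjects with no later C-SSRS lower the withdrawal-period suicidality percentages

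*Protocol*

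**What the plan says.** **Membership.** Protocol 15.3 admits dosed subjects who stop drug before Week 12, or who complete without entering the extension, "and have at least one assessment after the last dose of study medication for any safety or efficacy evaluation". SAP 6.1.9 has the same condition: "and have at least 1 assessment after the last study drug for any safety or efficacy evaluation". Neither asks for a Week 13-15 visit, a telephone contact or a minimum time off drug.

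**Timing of EOT.** Under Protocol 13.3, subjects who stop early "will be asked to return to the site and complete the EOT visit assessments". Protocol 7.1 asks them to "complete the End of Treatment visit as soon as possible following discontinuation of study drug and complete the 3 week withdrawal period". Protocol 7.1 also tells subjects to "administer study drug at approximately the same time each morning including on days when clinic visits occur", so a completer's Week 12 assessments can follow the last dose on the same day.

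**Withdrawal Baseline.** For data other than the diary, CSSA and DESS, and so for the C-SSRS, SAP Table 6.1 labels Days -5 to 3 from the last dose as Withdrawal Baseline and Days 4 to 10 as Withdrawal Week 1. For CSSA and DESS the baseline window ends on Day 1.

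**Denominators.** SAP 7.4.7.2 summarises C-SSRS categories by "treatment for any post-withdrawal baseline for withdrawal population". SAP 7.4.8.3.2 summarises ESAMs for the safety population and the "withdrawal population (withdrawal period), respectively". SAP 7.4.2 puts DEAEs on the Modified Withdrawal Population. Under SAP 6.1.9 that is the Withdrawal Population plus non-extension subjects who "do not enter the withdrawal period, but the last study dose dates are at least 2 days earlier than the last study visit".

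**The concern.** A percentage for a period should have as its denominator the subjects who could have been observed to have the event in that period. Under the literal rule, a subject who attends EOT shortly after stopping drug and has no later C-SSRS counts in the withdrawal suicidality table as a subject without an event. In fact nothing was observed after Withdrawal Baseline.

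Within an arm this can only lower the percentage. The table concerns suicidal ideation and behaviour after abrupt discontinuation, and Protocol 4.2 reports that the single SAE in the previous BED study was suicidal ideation.

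The SAP's own wording suggests that the literal reading was not intended, since its Modified Withdrawal Population is built to add subjects whom the literal rule already admits. Two programmers could therefore derive two different population flags from the same text.

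**Working it through.** The documents state no figure for this point, so there is none to reproduce. The check traces the rule through the visit windows and then sizes the effect under stated assumptions.

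**1. Who can be a case in SAP 7.4.7.2** (Table 6.1 windows, literal membership rule)

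| Contact after the last dose | In population? | Latest C-SSRS maps to | Can be a case? |
|---|---|---|---|
| EOT on Day 0-3, nothing later | Yes | Withdrawal Baseline | No |
| EOT on Day 0-3, then telephone calls only | Yes | Withdrawal Baseline | No; the calls in Protocol 11.8.10 do not include the C-SSRS |
| EOT on Day 4-10, nothing later | Yes | Withdrawal Week 1 | Yes |
| EOT on Day 0-3, then a Week 13 clinic visit | Yes | Withdrawal Week 1 | Yes |

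The first two rows are the problem.

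**2. Size for the C-SSRS.** Let f be the share of the denominator with no C-SSRS after Withdrawal Baseline, and r the rate among the others. Then reported rate = r x (1 - f). The documents do not give f. With r = 10% (assumed):

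- f = 5%: 10% x 0.95 = 9.5%
- f = 10%: 10% x 0.90 = 9.0%
- f = 20%: 10% x 0.80 = 8.0%
- f = 30%: 10% x 0.70 = 7.0%
- f = 50%: 10% x 0.50 = 5.0%

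For scale, the sample size section inflates 96 to 160 per arm for about 40% discontinuation: 96 / (1 - 0.40) = 160, and 160 x 0.40 = 64. If the population were only those 64 subjects, f of 5% to 50% would be 3.2 to 32 subjects per arm.

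**3. Between arms.** With r = 10% in both arms, f = 10% on placebo and 30% on dasotraline gives 9.0% and 7.0%, a ratio of 7.0 / 9.0 = 0.78. Reversing the shares gives 7.0% and 9.0%, a ratio of 1.29. Nothing in the documents favours either case.

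**4. The 2-day condition.** The Modified Withdrawal Population adds subjects whose last visit is at least 2 days after the last dose. Anyone assessed at that visit already has an assessment after the last dose, so is already in the Withdrawal Population. The addition is redundant, and subjects with 0-1 day off drug are also in through the base rule.

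**5. DEAEs.** A DEAE starts after the day of the last dose. A subject with 0 days off drug cannot have one recorded, and a subject with 1 day has almost no time at risk. These are the only subjects whom the base rule adds beyond what the 2-day condition intends. In the by-interval table, duration is last withdrawal visit minus last dose plus 1, so they have a duration of 1 or 2. They appear only in the 1-7 day row and are excluded from the 8-14 and 15-or-more rows.

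**6. ESAMs.** These are adverse events, and adverse events are recorded at EOT (Protocol 11.8.9). Events between the last dose and EOT can count, so r x (1 - f) overstates the loss. There is a separate inconsistency: SAP 6.1.9 excludes adverse event data from the main use of the Withdrawal Population, yet 7.4.8.3.2 uses that population for ESAMs.

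**The case against.** A reader might infer that subjects never seen off drug dilute the suicidality, DEAE and ESAM percentages alike, by something like 20% to 50%, and in the drug's favour. The documents do not support that:

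- DEAEs and ESAMs do not depend on a return visit, because events up to EOT count. The DEAE population was deliberately made wider to hold retrospectively collected events, and the by-interval DEAE table already limits its denominators by follow-up.
- SAP 6.1.1.2 starts the withdrawal period immediately after the last dose, and a late EOT supplies Withdrawal Week 1 data. Such subjects are seen in the period.
- Return rates after EOT appear nowhere, so neither a size nor a direction between arms can be claimed.

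It can also be said that the withdrawal objective in Protocol 5.3 names CSSA, DESS, HAM-A and MADRS. SAP 7.4.6 summarises these as scores with N by visit, so absent subjects do not dilute them. The withdrawal C-SSRS table is descriptive, since Fisher's exact test is planned only for the double-blind period. Suicidality found at EOT still counts in the double-blind summary (SAP Table 12). Disposition will show how many complete and discontinue the withdrawal period. Finally, the wording of the modified population suggests that the base population was meant to hold only subjects who entered the withdrawal period.

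All of this stands and narrows the point. It does not remove it: the literal rule still yields a C-SSRS denominator containing subjects who cannot be cases, and the disposition table does not identify them. An intention that must be inferred from a neighbouring definition is a reason to fix the text.

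**Conclusion.** The point holds for the withdrawal-period C-SSRS percentages. On the literal rule they are understated by the factor 1 - f, where f is the share of the Withdrawal Population with no C-SSRS after Withdrawal Baseline. An r of 10% becomes 9.5% to 5.0% if f is 5% to 50%; that range is an assumption, and f could be smaller. Any effect on the comparison between arms depends on how f differs by arm, and its direction is unknown.

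For ESAMs the understatement is partial. For overall DEAEs it is limited to subjects with 0-1 day off drug. CSSA, DESS, HAM-A and MADRS score summaries are not diluted. This is a definitional gap in descriptive safety tables; the documents do not show how large the dilution will be in practice.

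**What to change.** 1. In Protocol 15.3 and SAP 6.1.9, define the Withdrawal (Safety) Population as dosed non-extension subjects with at least one clinic or telephone assessment after Withdrawal Baseline as windowed in SAP Table 6.1. The anchor should not be the EOT visit, so that an EOT on Day 4 or later still counts.
2. In SAP 7.4.7.2, use as denominator the subjects with at least one post-withdrawal-baseline C-SSRS. The first change does not achieve this alone: a subject can qualify through a telephone contact, or through a CSSA or DESS on Day 2 or 3, without a C-SSRS after Day 3. State also whether Table 6.1 or Table 12 governs a C-SSRS from an EOT on Day 4 or later, because Table 12 assigns visits through EOT to the double-blind period.
3. Keep the Modified Withdrawal Population for adverse events. With the first change its 2-day condition takes effect: EOT-only subjects with 0-1 day off drug leave the DEAE denominator and the intended ones stay.
4. Reconcile the ESAM population in SAP 7.4.8.3.2 with the exclusion of adverse event data in 6.1.9.
5. Report by arm the number of non-extension subjects with no assessment after Withdrawal Baseline. The restricted denominator describes only those observed and does not correct for informative loss, so the reader needs this count.

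The cost is revised wording and a population flag, set before database lock, with no new data. Denominators become smaller and the descriptive rates slightly less favourable.
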